7.2. Treatment Exposure

Exposure will be derived for RP-6306 and FOLFIRI respectively.

Duration of Exposure for each drug RP6306 and FOLFIRI will be defined as the duration between the first and last doses of respective study drug

- Duration of RP6306 exposure = last dose date first dose date + 1.
- Duration of FOLFIRI exposure = last infusion date first infusion date + 14, due to 2 week infusion cycle

Overall duration of treatment for the study regimen is defined as Date of Treatment Discontinuation (from EOT page in the CRF) – first dose date +1. If treatment is still ongoing, use cut off date. If Date of Treatment Discontinuation is not collected, use the duration of exposure calculated above (take the longer of the either drugs)..

The last dose date will be obtained from the end of treatment (EOT) CRF page for each study drug. Number of days dosed will be derived as the number of days a patient received a dose of each study drug (i.e., excludes off treatment days and any missed doses).

Dose intensity for RP-6306 will be derived as:

Dose intensity = (total dose received/total planned dose)*100%

Total dose received (mg) for RP6306 is the sum of total doses (mg) received. If a patient had a dose reduction/change during treatment, then the total dose received will be calculated for each actual dose received and then summed to give the total dose received.

Total dose received: $\sum_{i=0}^{k}$ number of days dosed at dose $x_i * dose x_i$

for i = 1 to k where i represents the number of dose levels received and k = number of distinct dose levels

Total planned dose for RP6306 will be derived as initial assigned dose a patient will receive without any interruptions or reductions based on the time-period between the date of first dose and date of last dose after excluding days when dosing information is not available, accounting for the number of treatment days per week. This is assuming the days without dosing information is missing at random.

A dose interruption will be defined as a planned interruption where a decision is made to interrupt the dose temporarily, usually due to AE reason. Dose interruptions will be captured on the eCRF.

A dose reduction is any reduction prescribed by PI in dose/schedule compared to the initial dose.

Patients who do not have an end of treatment date in the eCRF at the time of analysis and reporting will be considered ongoing treatment. For deriving exposure, ongoing patients will be assumed to be ongoing at the date of the data cut off and therefore the data cutoff date will be used to derive exposure.

Exposure for RP6306 will be listed and summarized by the Safety Population and presented by module 1a and 1b and dose/schedule.

The following will be presented for RP-6306 (if applicable)

- Duration of exposure (days)
- Number and % of patients with at least 1 cycle, with at least 2 cycles...etc (up to at least 5 cycles).
- Number of cycles treated (completed)
- Total dose received (mg)
- Dose intensity based on initial planned dose (%)
- Number and % of patients with at least one dose interruption reported in dosing log by considering only those incidences when AE is indicated as a reason
 - Further broken down by number with 1, 2 or \geq 3 interruptions
- Number and % of patients with at least one dose reduction (include dose reduction as a result
 of schedule change with less dose intensity) reported in dosing log considering only those
 incidences when AE is indicated as a reason
 - Further broken down by number with 1, 2 or \geq 3 reductions
- Number of patients with any dose escalation per protocol

Patients with both an interruption and reduction will be included in both the interruption and reduction summaries.

The following will be presented for FOLFIRI.

• Duration of exposure (days)

• Number of infusions received

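### FOLFIRI exposure credits a full two-week cycle with no cap, so it can run past the data cutoff (13 days on the plain reading) or past death

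*SAP*

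**What the plan says.** SAP Section 7.2 (Treatment Exposure) covers both drugs: "Exposure will be derived for RP-6306 and FOLFIRI respectively". Exposure for each drug "will be defined as the duration between the first and last doses of respective study drug". Two formulas follow. In both, the minus sign between the dates is missing from the text available to me, and I read it as a subtraction:

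- RP-6306: "Duration of RP6306 exposure = last dose date first dose date + 1"
- FOLFIRI: "Duration of FOLFIRI exposure = last infusion date first infusion date + 14, due to 2 week infusion cycle"

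A patient with no end-of-treatment date in the eCRF counts as ongoing, and the rule is that "ongoing patients will be assumed to be ongoing at the date of the data cut off and therefore the data cutoff date will be used". The sentence does not mention FOLFIRI separately.

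Overall regimen duration runs from first dose to treatment discontinuation with + 1. For patients not yet off treatment the instruction is "If treatment is still ongoing, use cut off date". If the discontinuation date was not collected, the instruction is to "use the duration of exposure calculated above (take the longer of the either drugs").

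The FOLFIRI summaries listed in Section 7.2 are two: duration of exposure and number of infusions.

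**The concern.** The + 14 makes sense when the date entered is a real infusion: it credits the two-week cycle which that infusion opens. A data cutoff date is not an infusion and already includes the time since the last one. Adding a cycle to it counts days that have not yet been observed. The same happens after a death, because the credited cycle is not cut short.

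The SAP limits dates of this kind elsewhere. Sections 5.3.1, 5.3.2 and 5.3.4 replace an imputed stop date later than death by the death date. Section 5.3.5 holds an imputed last dose date to the earliest of itself, study discontinuation and data cutoff. That last limit applies only to imputed dates and acts before the + 14 is added, so it does not help here.

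At stake is the accuracy of one of only two FOLFIRI exposure summaries. It could report a longer exposure than the patient's time under observation or time alive.

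**Working it through.** Inputs, from SAP Section 7.2 unless stated: the FOLFIRI formula (+ 14), the RP-6306 formula (+ 1, an inclusive day count), the cutoff rule for ongoing patients, and the 14-day cycle (SAP Section 3.2). Day 1 is the first infusion.

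**Step 1: the plan's own convention.** With k infusions on schedule, the last falls 14(k − 1) days after the first. The formula gives 14(k − 1) + 14 = 14k days: 14 for one infusion, 28 for two, 84 for six. The + 14 therefore reproduces whole cycles and is internally coherent for a real infusion date. It counts the infusion day plus 13 more.

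**Step 2: ongoing patient, cutoff C entered as the end date.** The formula gives C − first + 14. The inclusive count to the cutoff is C − first + 1. The difference is 14 − 1 = 13 days, however long ago the last infusion was.

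**Step 3: ongoing patient, actual last infusion date L entered.** For a cutoff d days after L, the overrun is (L − first + 14) − (L + d − first + 1) = 13 − d days for d from 0 to 13, and none after that.

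Example with six infusions on schedule, the sixth on Day 1 + 5 × 14 = Day 71:

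| Days from sixth infusion to cutoff | Days actually elapsed | Cutoff in formula | Overrun | Actual last infusion in formula | Overrun |
|---|---|---|---|---|---|
| 0 | 71 | 84 | 13 | 84 | 13 |
| 7 | 78 | 91 | 13 | 84 | 6 |
| 13 | 84 | 97 | 13 | 84 | 0 |

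**Step 4: death d days after the last infusion.** Days credited after death are max(0, 13 − d): 13 for d = 0, 10 for d = 3, 6 for d = 7, and 0 for d = 13. A patient with one infusion who dies 3 days later has 14 days of FOLFIRI exposure against 4 days alive on study.

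**Step 5: with a cap at death and cutoff.** The three patients in the table get 71, 78 and 84 days. In Step 4 the cap removes 13, 10, 6 and 0 days. Nothing changes for a patient who completes the credited cycle before death or cutoff.

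**The case against.** The strongest reply is that the SAP never writes out the FOLFIRI formula for ongoing patients. It ties the + 14 to the infusion cycle, and for the overall regimen it pairs the cutoff with + 1. A programmer could therefore use cutoff − first + 1, which has no overrun. This stands to the extent that a reader should not infer exactly 13 extra days for every ongoing patient. The 13 days depend on putting the cutoff in place of the last infusion date. Section 7.2 also takes the last dose date separately for each drug, so a patient who has stopped only FOLFIRI may have a real date. It does not dispose of the point: the plain reading gives 13 days, using the actual infusion date gives 0 to 13, and the overrun past death arises on any reading.

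The second reply is that crediting a full cycle to a two-weekly drug is a legitimate convention, and that it need not match the convention for a drug taken daily. That stands. The + 14 is not an arithmetic error.

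The third is that little depends on the figure. That also stands. The number of infusions is unaffected, dose intensity is defined only for RP-6306, and no interim analysis is planned (SAP Section 11). The documents do not say how many patients will be ongoing at the cutoff, and it may be few.

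A stronger reading is tempting for CBR, which counts at least 16 weeks on treatment without progression. With a last infusion on Day 99 and a last RP-6306 dose on Day 100, the fallback for overall duration gives 99 − 1 + 14 = 112 days, exactly 16 weeks. The documents do not support this as a harm. SAP Section 8.1.4 does not refer to Section 7.2. A patient with no end-of-treatment date is treated as ongoing, so the fallback would rarely be reached. Day 99 is the eighth infusion on schedule, and 112 days is the intended eight cycles. The capped rule would also give 112 unless death or cutoff came earlier.

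**Conclusion.** The concern holds as a minor defect of definition. As written, the FOLFIRI duration can include days after the data cutoff or after death. For an ongoing patient the overrun is 13 days if the cutoff stands in for the last infusion date, and 13 − d days (d from 0 to 13) if the actual infusion date is used. For a patient who dies fewer than 13 days after an infusion it is 13 − d days. It never exceeds 13 days per patient.

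The consequence is confined to the descriptive FOLFIRI duration and, in rare cases, to overall duration through the longer-of-two-drugs fallback. DLTs, MTD, ORR and PFS do not draw on it.

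The 13-day figure assumes that the general sentence on ongoing patients applies to FOLFIRI in the form written. The case of death needs no such assumption.

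**What to change.** In SAP Section 7.2, replace the FOLFIRI line with:

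FOLFIRI exposure = min(actual last infusion date + 13, death date, data cutoff date) − first infusion date + 1.

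State that the actual last infusion date is used for ongoing patients too, so that the cutoff acts only as a cap. This keeps the two-week convention. Whether to cap at treatment discontinuation as well is a choice of convention: with one infusion and discontinuation recorded the same day, such a cap would give 1 day. The SAP should say which is meant. It would also help to reword the opening definition, which describes exposure as running only from first to last dose, so that it agrees with the credited cycle.

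The cost is one line of SAP text and the matching program code, with no new data. The reported FOLFIRI durations become slightly shorter.

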If anti-tumor activity is observed at a dose level that is lower than the current dose level being explored (after escalation has proceeded to a higher dose level), additional patients (N≤6), preferably with the same tumor/genomic alteration, may be enrolled at the lower dose level to further confirm safety and efficacy at that dose level. The relevant DLTs from the backfill cohorts will be included in the MTD and RP2D determination by the SRC. Additionally, intrapatient dose escalations for patients at a lower dose level will be allowed at the discretion of the Investigator, and with Sponsor approval and guidance by the SRC, if the higher dose level was deemed safe by the SRC.

Figure B: Module 1a and 1b Escalation Schema Module 1a: RP-6306 + FOLFIRI **MTD** Module 1b: RP-6306 + FOLFIRI Dose Finding (14 Day Cycles) Dose Finding (14 Day Cycles) RP-6306 Continuous QD FOLFIRI Days 1 and 2 RP-6306 3 Days On / 4 Days Off FOLFIRI Days 1 and 2 **MTD** Level R: DLT Safety or intolerability Cohort sizes at each dose level will be guided by BOIN drug combination criteria Cohort sizes at each dose level will be guided by BOIN drug combination criteria

BOIN=Bayesian optimal interval; DLT=dose-limiting toxicity; MTD=maximum tolerated dose;

Table A: **Dose Escalation Tables**

(A1) Dosing Regimens for Module 1a (Continuous RP-6306)^a

Treatment Frequency	Drug	Route of Administration	Dose Level 1 ^b (Starting Dose)	Dose Level 1 ^b and above	Dose Level R	Dose Level R+1°	Dose Level R+N ^c
Once Daily	RP-6306	Oral	40 mg	120 mg, then escalation up to 100%	Same as Current Dose Level	Per BOIN rules up to 20%-50% increase or MTD in MYTHIC	Per BOIN rules up to 20%-50% increase or MTD in MYTHIC
	Irinotecan	IV over 30-90 min	180 mg/m^2	180 mg/m^2	Same as Current Dose Level	Up to 180 mg/m ²	Up to 180 mg/m²
FOLFIRI	Leucovorin	IV over 30-90 min concurrently with irinotecan	400 mg/m ²	400 mg/m ²	Same as Current Dose Level	400 mg/m ²	400 mg/m^2
once every 2 weeks on	Fluorouracil	IV bolus after leucovorin	400 mg/m^2	400 mg/m^2	Same as Current Dose Level	400 mg/m ²	400 mg/m^2
Day 1 ^d				THEN			
	Fluorouracil	IV continuous infusion; start on Day 1 over 46 hours only	2400 mg/m ²	2400 mg/m ²	Same as Current Dose Level	2400 mg/m ²	2400 mg/m ²
1	* If Dose Level 1 is not tolerated						

	II Dose Level I is not tolerated					
Treatment Frequency	Route of Administration	Drug	Dose Level 1D ^c	Dose Level 2D ^c	Dose Level 3D ^c	
Once Daily	Oral	RP-6306	40 mg	40 mg	40 mg	

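### RP-6306 dose reductions and dose intensity are referenced only to the initial dose, so after intrapatient escalation the exposure tables can miss an AE-driven cut and show intensity above 100%

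*SAP*

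**What the plan says.** SAP section 7.2 (Treatment Exposure) defines a reduction by reference to the starting dose: "A dose reduction is any reduction prescribed by PI in dose/schedule compared to the initial dose". Dose intensity is a ratio, "Dose intensity = (total dose received/total planned dose)*100". Its numerator follows the patient through every level: "the total dose received will be calculated for each actual dose received and then summed to give the total dose received". Its denominator does not: "Total planned dose for RP6306 will be derived as initial assigned dose a patient will receive without any interruptions or reductions", taken over the period from first to last dose and excluding days without dosing information. The table shell lists one version only, "Dose intensity based on initial planned dose". It also has a row headed "Number and % of patients with at least one dose reduction", restricted to entries in the dosing log with an AE as the reason, and a count of patients who escalated.

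Escalation within a patient is planned. The protocol synopsis (Dose Finding) says that "intrapatient dose escalations for patients at a lower dose level will be allowed at the discretion of the Investigator", with sponsor approval and SRC guidance. The Module 1a text lets Dose Level 1 patients move from 40 mg to 120 mg once daily after the next level has cleared its DLT period, and SAP section 3.2.1 repeats this. The synopsis section on dosage and administration allows reductions and interruptions for toxicity.

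Neither definition in SAP 7.2 resets its reference after an escalation. Patients stay in the column of the initial dose received (SAP section 4, closing sentence).

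For the chemotherapy, the list that begins "The following will be presented for FOLFIRI" contains only duration of exposure and number of infusions.

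**The concern.** The numerator of dose intensity rises with escalation and the denominator stays at the starting dose. Once a patient has escalated, the ratio no longer shows how much of the intended dose was taken. The reduction count has the same reference, so a cut made because the higher dose was not tolerated is not a reduction unless it takes the patient below the starting dose.

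The DLT window covers only the first 28 days. Later tolerability has to be read from descriptive outputs such as reductions, interruptions and intensity. An escalated patient who needed a cut is informative about the higher dose, yet would appear in the lower-dose column with no reduction and an intensity well above 100%, which also raises that column's mean.

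**Working it through.** The documents give no dose-intensity figure to reproduce, so the check applies the SAP formula to example patients.

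**Inputs from the documents:** 40 mg and 120 mg once daily, continuous (protocol synopsis, Module 1a); the definitions in SAP 7.2.

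**Assumptions:** all durations, and the dose after the cut. The documents supplied give no individual reduction steps. The example doses are arithmetic only and imply nothing about patient management.

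**Formulas**
- SAP intensity = 100 × Σ(days dosed × dose) / (initial dose × days in period)
- Escalation-adjusted intensity = same numerator / Σ(days × planned dose), where planned dose is the initial dose until escalation and the escalated dose from then on

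**1. Main example:** 40 mg × 56 d, 120 mg × 56 d, then an AE-driven cut to 80 mg × 28 d.
- Received: 40×56 + 120×56 + 80×28 = 2,240 + 6,720 + 2,240 = 11,200 mg
- SAP planned: 40×140 = 5,600 mg; intensity 11,200/5,600 = 200%
- SAP reductions: 80 mg is above 40 mg, so 0
- Adjusted planned: 40×56 + 120×84 = 2,240 + 10,080 = 12,320 mg; intensity 11,200/12,320 = 90.9%, with 1 reduction

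**2. Range:** 28 to 84 days at 40 mg, 28 days at 120 mg, then 28 days at 40, 60, 80 or 90 mg. The SAP rule gives 140.0% to 208.3% and no reduction in every case. The adjusted rule gives 71.4% to 91.7% and one reduction in every case.

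**3. Missed doses:** 40 mg × 56 d, then 28 days at 120 mg with half the doses missed.
- Received: 40×56 + 120×14 = 3,920 mg
- SAP: 3,920/(40×84) = 3,920/3,360 = 116.7%
- Adjusted: 3,920/(40×56 + 120×28) = 3,920/5,600 = 70.0%

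**4. Control without escalation:** 120 mg × 28 d, then 80 mg × 28 d.
- Received: 3,360 + 2,240 = 5,600 mg; planned on either basis 120×56 = 6,720 mg
- Intensity 83.3% and 1 reduction under both rules. The problem is confined to escalated patients.

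**5. How large a cut can go uncounted:** after an increase by a fraction r, a cut by a fraction f stays at or above the initial dose when (1 + r)(1 − f) ≥ 1, that is f ≤ r/(1 + r).
- 40 to 120 mg (r = 2): cuts up to 66.7%
- r = 1: up to 50%
- r = 0.5: up to 33.3%
- r = 0.2: up to 16.7%

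The last three use the protocol's step sizes: up to 100% before Level R and 20% to 50% after it.

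**The case against.** The strongest reply is that the SAP is consistent. It presents patients by initial dose throughout, labels the intensity row accordingly, and counts escalated patients separately. This stands in part: a value above 100% is valid for a measure so labelled, and a reader who infers that such a value is an error would be wrong. The gap is that no measure against the escalated dose accompanies it.

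Second, the toxicity is not lost. SAP section 7.1 tabulates TEAEs leading to dose modification, and summarizes or lists those leading to reduction by preferred term, without relying on the 7.2 definition. A reader might infer that such cuts vanish from the report; the documents do not support that. What remains is that the exposure and AE tables could disagree about the same patient. The AE overview row also merges reductions with interruptions.

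Third, the reduction row draws on the dosing log, so a programmer might count a logged cut from 120 to 80 mg. That stands as an ambiguity: the only definition given excludes it, and the two texts need reconciling.

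Fourth, interruptions have their own patient count, which a high intensity elsewhere cannot offset. Only the mean intensity of a column is affected.

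Fifth, the threefold step is the largest specified, in a cohort that starts with up to 2 patients, and later steps are smaller. This is fair, and step 5 of the working shows the uncounted range shrinking accordingly.

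Finally, a reader might infer that the MTD or RP2D would be wrong. The MTD rests on 28-day DLTs, and the RP2D on the totality of safety, PK, pharmacodynamic and efficacy data. No text makes these exposure rows a decision rule.

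**Conclusion.** The point holds for escalated patients in the descriptive RP-6306 exposure tables. Under the stated definitions, an AE-driven cut that remains at or above the starting dose is not a reduction, and intensity can exceed 100% while cuts or missed doses occur at the escalated level. The main example gives 200% and 0 reductions, against 90.9% and 1. The example sizes rest on assumed durations and cuts; the direction follows from the wording.

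A cut below the initial dose is still counted. Non-escalated patients, DLT counts, MTD rules and sample size are unaffected. The overall effect depends on how many patients escalate, which the documents do not give.

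The absence of irinotecan and fluorouracil intensity is a lesser matter. AE-driven changes to study treatment already have an output in SAP 7.1, so extra FOLFIRI rows would be a useful addition, not the correction of an error.

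**What to change.** In SAP section 7.2:

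1. Define a reduction as an AE-driven decrease from the dose or schedule in force immediately before it, and make the dosing-log row use that definition.
2. Keep dose intensity on the initial planned dose, and add a second version. Its planned dose equals the initial dose until a protocol-allowed escalation and the escalated level from then on, and is not lowered by later toxicity-driven reductions or interruptions.

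The last condition matters. A denominator that followed every prescribed change would give 11,200/11,200 = 100% in the main example. It would also give 5,600/5,600 = 100% instead of 83.3% in the non-escalated control, hiding ordinary reductions.

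Optional: add dose reductions and dose intensity for irinotecan and fluorouracil.

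The cost is a few sentences of SAP text and minor programming from dosing logs already collected. No dose or clinical rule changes.

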7.3. Laboratory Evaluations

All laboratory data recorded in the eCRF will be listed. Out-of-reference range values will be flagged as high (H) or low (L) in the listings. The results in standard unit will be used in the summary tables.

Box plots for percent changes from baseline over time for lab parameters will be produced by for all treated patients, based on the safety population and the number of patients with data at the relevant timepoints from selected lab tests. Sample size for each timepoint will be displayed. Summary tables of actual and change from baseline from all the numerical lab tests will be provided.

Selected laboratory assessments (hemoglobin, neutrophils, white blood cells [WBC], platelets, ALT, AST, BUN, total bilirubin, and creatinine) will be also presented in shift tables showing baseline grade vs. maximum grade on study for lab assessment with CTCAE grading, based on all post-baseline data including unscheduled assessments. The denominator for each on-treatment maximum grade is the total number of patients in the corresponding row for baseline grade (i.e., the baseline row totals). The shift from baseline to worst value will be summarized.

For lab assessments which do not have CTCAE grading these will be categorized as low/normal/high based on reference ranges and shifttables will present baseline versus worst value on study.

If worst criteria could be a low or a high value or an increase or decrease (i.e., in both directions) then shift tables should be split to show shift from baseline to worst low/decrease value and then repeated for worst high/increase value. For example, CTCAE grade criteria is given for both lymphocytes count increased and lymphocyte count decreased.

Table 3: Clinical Safety Laboratory Analytes from the Protocol

Hematology	Serum Chemistry	Urinalysis
 White blood cell count with differential (including at minimum: neutrophils, basophils, eosinophils, lymphocytes, monocytes) RBC count Hemoglobin Hematocrit Platelet count 	 Albumin Alkaline phosphatase ALT AST BUN and/or urea Calcium Chloride Creatinine Glucose Lactate dehydrogenase Phosphate or phosphorus Potassium Sodium 	 Specific gravity Leukocyte esterase Ketones Protein Glucose Nitrite Occult blood Microscopy (if clinically indicated) pH

Hematology	Serum Chemistry	Urinalysis
	Direct bilirubin	
	Total protein	
	Uric acid	

Abbreviations: ALT = alanine aminotransferase; AST = aspartate aminotransferase; BUN = blood urea nitrogen

Post-baseline liver function tests including unscheduled assessments will be summarized in the following categories in Safety Population. Corresponding listing will be produced to assess clinical relevance of these events (some maybe due to underlying disease):

- AST $> 3 \times ULN$ or $3 \times Baseline$ (if baseline value is >ULN)
- ALT $> 3 \times ULN$ or $3 \times Baseline$ (if baseline value is >ULN)
- ALP $> 3 \times ULN$ or $3 \times Baseline$ (if baseline value is >ULN)
- Total bilirubin > 2 × ULN

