Study evaluations and procedures will occur as outlined in the Schedules of Assessments (refer to Section 12.1). The study will consist of a Screening Period (Day -28 to Day -1) to determine eligibility, a Treatment Period (14-day cycles), an End-of-Treatment (EOT) Period (occurring within 7 days after the last dose of study treatment), a Safety Follow-up Period (occurring 30 days ±2 weeks after the last dose of study treatment for all patients who are not cleared at the EOT visit, including patients with ongoing Grade ≥2 drug-related toxicities at the EOT visit), and a Survival Follow-up (every 3 months ±2 weeks for up to 12 months). The End of Study is defined as the date of the last visit (including all follow-up visits up to 12 months) of the last patient in the study. Patients will be followed for survival up to 12 months after EOT unless the patient withdraws consent to the study, the study is terminated, the patient dies or is lost to follow-up (LTFU).

Safety:

Safety and tolerability will be reported by the Investigator and evaluated by the Medical Monitor, Safety Officer, and SRC throughout the study. Assessments will include AEs, TEAEs, serious adverse events (SAEs), treatment discontinuations or dose modifications due to AEs, DLTs, changes in Eastern Cooperative Oncology Group (ECOG) performance status, changes in clinical laboratory results (hematology, chemistry, and urinalysis), vital signs, observations during physical examination (PE), ECGs, and others. All treatment-related AEs should be followed until resolution or documented Investigator decision stating that further improvement is not expected.

Efficacy:

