7.1. Adverse Events

Adverse events (AEs) will be coded using the Medical Dictionary for Regulatory Activities (MedDRA) version 26.0 or more recent version (at the time of database lock) and graded according to NCI-CTCAE version 5. All laboratory test results will be classified for toxicity grade according to the NCI-CTCAE version 5 criteria.

DLTs will be listed and summarized based on the DLT Evaluable Population.

Treatment emergent adverse events (TEAEs) are those events that occur or worsen on or after the first dose of study drug up through 30 days post the last dose. Those events occurred after start of subsequent anticancer therapy will be excluded.

An overview summary table of the number and percentage of patients in each of the categories listed below will be presented. This summary will be presented based on all patients in the study (overall summary to summarize unique patients) and then repeated split by module 1a or 1b and dose/schedule (see Section 5.1 for general presentation format).

- All TEAEs
- Treatment related TEAEs (related to either study drug)
- DLTs
- TEAEs with \geq CTCAE Grade 3
- Treatment-related TEAEs with \geq CTCAE Grade 3 (related to either study drug)
- Serious TEAEs
- Treatment-related serious TEAEs (related to either study drug)
- TEAEs with outcome of death
- TEAEs leading to discontinuation of study treatment
- TEAEs leading to dose modification (i.e., dose reduced or dose interrupted) of study treatment

TEAEs will be summarized by system organ class (SOC), preferred term (PT), and by NCI CTCAE toxicity grade (where applicable). For summary tables, an AE that occurs more than once within a SOC and/or PT for the same patient will be counted only once using the worst NCI toxicity grade experienced.

Number and percentage of participants with TEAEs will also be presented by PT only. This summary will be sorted in decreasing order of frequency based on overall safety population.

For the summary tables related to toxicity grades, if there are two or more TEAEs (or AEs) with same SOC or PT and different toxicity CTCAE grades for the same subject, only the maximum toxicity grade of AE be counted.

Data listing will be provided for all TEAEs, TEAEs with ≥ CTCAE Grade 3 and serious TEAEs.

An AE table of most frequently occurring TEAEs, showing all events in at least 5% of patients, will be summarized by preferred term, by decreasing frequency based on all patients. This cut-off may be modified after review of the data.

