7.6. Physical Examination and ECOG Performance Status

Abnormalities identified from physical examination will be listed for the safety analysis set.

Shift table of baseline ECOG performance to worst post-baseline status will be summarized as the number and % of patients in each ECOG category based on the Safety Population.

Any change in PE findings assessed as clinically significant should be recorded as an AE or SAE.

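### Worst-value laboratory, liver, BP, QTcF and ECOG summaries have no end of window, while the TEAE tables stop at 30 days after last dose and at subsequent anticancer therapy

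*SAP*

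**What the plan says.** SAP 7.3 plans shift tables "showing baseline grade vs. maximum grade on study for lab assessment with CTCAE grading", "based on all post-baseline data including unscheduled assessments". The next sentence gives the same quantity another name: "The denominator for each on-treatment maximum grade is the total number of patients in the corresponding row for baseline grade". Laboratory tests without CTCAE grading get tables that "will present baseline versus worst value on study". For the liver categories, "Post-baseline liver function tests including unscheduled assessments will be summarized". None of these statements has an end date.

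The same openness runs through the following sections. The BP categories in SAP 7.4 and the QTcF categories in SAP 7.5 count a patient who meets the criterion at any post-baseline assessment, unscheduled ones included. SAP 7.6 plans a "Shift table of baseline ECOG performance to worst post-baseline status". SAP 5.2.1 defines baseline but sets no end to the post-baseline period.

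SAP 7.1 does set limits for adverse events. The treatment-emergent window ends 30 days after the last dose, and of later events it says: "Those events occurred after start of subsequent anticancer therapy will be excluded".

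The Protocol Synopsis (General Study Conduct) places Safety Follow-up at "30 days ±2 weeks after the last dose of study treatment for all patients who are not cleared at the EOT visit".

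**The concern.** The two parts of the safety analysis use different windows without saying so, and SAP 7.3 names its own window in two incompatible ways. Two programmers could follow the text and produce different tables.

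A worst-value table keeps a single late extreme permanently. If a patient has a first Grade 4 neutropenia under the next chemotherapy, SAP 7.3 as written shows it as that patient's maximum grade in the RP-6306 + FOLFIRI dose group, while SAP 7.1 keeps the event out of the TEAE tables.

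Laboratory assessments are part of the primary safety endpoint, SAP 2.2.1 lists CTCAE-graded laboratory toxicities among the safety endpoints, and the RP2D is to rest on the totality of the data, safety included. Dose groups are small, so one patient can visibly change a percentage.

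**Working it through.** The plan states no figure for this point, so there is none to reproduce. The check compares the windows, then computes the overlap in days, then gives an illustration on assumed inputs.

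**1. Windows side by side**

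| Summary | End of window | Cut at subsequent anticancer therapy |
|---|---|---|
| TEAEs (SAP 7.1) | 30 days after last dose | Yes |
| Concomitant medications (SAP 6.6) | 30 days after last dose | Yes, if earlier |
| ORR (SAP 8.1.2) | Progression | Yes |
| Tumour size (SAP 8.1.1, 8.1.7) | Progression or last evaluable assessment | Yes |
| Laboratory shift tables, graded and ungraded (SAP 7.3) | None | No |
| Liver categories (SAP 7.3) | None | No |
| BP and QTcF categories (SAP 7.4, 7.5) | None | No |
| Worst ECOG (SAP 7.6) | None | No |

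The worst-value safety summaries are the exception, and the SAP gives no reason for it.

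**2. Overlap with Safety Follow-up**

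- Permitted visit days after last dose: 30 − 14 = 16 to 30 + 14 = 44, which is 44 − 16 + 1 = 29 days.
- Days beyond the TEAE limit: 44 − 30 = 14.
- Share of permitted days beyond the limit: 14/29 = 48%. This is a share of days, not of visits. The nominal visit is day 30, inside the TEAE window.
- A value before day 30 is also outside the TEAE rule if new therapy has already started. Nothing in the text available ends Safety Follow-up at that point.

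**3. Other sources of late values**

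The Protocol Synopsis (Safety) follows AEs until, among other endpoints, abnormal laboratory values normalise, stabilise or return to baseline, and SAP 7.3 expressly admits unscheduled draws. Survival Follow-up is by telephone or the centre's standard method, with no laboratory draw stated.

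**4. Illustrative size (all three inputs assumed)**

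Let p be the share of patients who already reach the grade of interest inside the TEAE window, f the share with any value outside it, and q the chance that such a value is the first to reach that grade. The added share of patients is (1 − p) × f × q.

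- Low: p = 0.5, f = 0.1, q = 0.05 gives 0.5 × 0.1 × 0.05 = 0.0025, or 0.25 percentage points (0.26 of 104 patients).
- Middle: p = 0.3, f = 0.2, q = 0.1 gives 0.7 × 0.2 × 0.1 = 0.014, or 1.4 points (about 1.5 of 104).
- High: p = 0.1, f = 0.4, q = 0.2 gives 0.9 × 0.4 × 0.2 = 0.072, or 7.2 points (about 7.5 of 104).

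Within one dose group the effect comes in whole patients. With 6 patients sharing the same baseline grade (assumed), one added case moves 1/6 (16.7%) to 2/6 (33.3%). That is an extreme, not an expected value.

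**The case against.** The strongest reply is that the effect is unproven and probably small. The Schedule of Assessments is not in the text available, so it cannot be confirmed that laboratory tests, ECGs or ECOG are recorded at Safety Follow-up. Continued follow-up of an abnormal value usually documents its resolution, after the worst grade has already been counted; only a new, higher grade changes the table. All laboratory data are listed, and the liver table has its own listing for judging clinical relevance. This stands as a limit on size. It does not remove the contradiction in SAP 7.3, and a listing does not correct a summary table.

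A second reply concerns the remedy. A value on days 31 to 44 without new therapy may be a delayed study-drug effect, and the protocol asks for possibly related AEs to be reported beyond the usual period. The cut at new therapy is therefore better supported than the 30-day cut. This stands, and is why later values should be flagged in the listings.

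A reader might also infer four stronger things that the documents do not support:

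- *That dose finding is distorted.* The MTD rests on DLTs in the first 28 days, which this window does not touch. No rule ties the RP2D to the shift tables.
- *That the tables attribute late values to study treatment.* They are descriptive and assign no causality; they only place the value under the dose group.
- *That only patients with unresolved toxicity are followed longer.* The text covers patients not cleared at EOT, of whom those with ongoing Grade ≥2 drug-related toxicity are one part. A 30-day cut would not fully even out ascertainment either.
- *That laboratory and AE tables would otherwise agree.* The protocol records as AEs only laboratory abnormalities that lead to treatment modification or need intervention, so the two differ by design.

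**Conclusion.** The point holds as a defect in the analysis rule. SAP 7.3 states an open-ended window, labels the result as if it were restricted, and departs from the limits in SAP 7.1; SAP 7.4 to 7.6 share the open end. Followed literally, any value recorded after new anticancer therapy starts, or after day 30, can become the worst value shown for the assigned dose group.

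Its size cannot be read from the documents. Certainty that late values will exist is not supported; the number is probably small. The range of 0.25 to 7.2 percentage points rests wholly on assumed p, f and q. The change should be made because the text is contradictory and the correction is cheap, not because a large distortion has been shown.

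**What to change.** Define *on-treatment* once in the SAP, for example in 5.2.1: from first dose through the earlier of 30 days after last dose and the start of subsequent anticancer therapy, which is the SAP 7.1 window. Apply it to every worst-value and any-post-baseline summary in 7.3 to 7.6: graded and ungraded laboratory shifts, liver categories, BP, QTcF and ECOG. Replace the *on study* wording in 7.3 with the defined term.

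Keep later values in the listings with two separate flags, one for values after the window and one for values after new therapy. Possible delayed effects on days 31 to 44 in patients without new therapy then remain visible.

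The cost is one definition, matching wording in four sections, and a date filter already needed for TEAEs; SAP 5.3.4 and 5.3.5 already cover partial dates for subsequent therapy and last dose. The downside is that a few late values, some possibly delayed study-drug effects, move from the tables to the listings.
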